Clinicians at TRI will record distance walked, rest periods, exercising heart rate (as palpated by the radial pulse), ratings of perceived exertion and ratings of pain severity on a scale of 0 (no pain) to 10 (worst imaginable pain) (Hawker, Mian, Kendzerska, & French, 2011) for each exercise session at TRI. Patients will self-record their other exercise sessions on a weekly basis using standard exercise diaries. Frequency, time, type, exercising heart rate and rating of perceived exertion will be recorded for each exercise session outside of TRI. Patients will wear a non-invasive heart rate monitor (Polar) while walking at the 2nd week, 3rd month and 6th month mark of the program to help determine acute responses to aerobic exercise. Average exercising heart rate will be measured and recorded. VO2peak, 6MWT, QOL (SF-36), and walking impairment (WIQ) will be re-assessed at the 3 month and 6 month mark of the program.

Training volume will be quantified for each group for the prescribed and actual exercise load. For aerobic exercise, training will be calculated as the product of intensity in heart rate reserve, duration, and frequency for both the prescribed and actual exercise. For resistance exercise, training will be calculated as the product of weight, numbers of sets, and number of repetitions for each exercise for both prescribed and actual exercise.

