## Comparing the efficacy of cardiac rehabilitation for patients with peripheral artery disease to patients with coronary artery disease/Protocol #03

### 4.7 A description of the "stopping rules" or "discontinuation criteria"

Participants can choose to withdraw from the study at any time. If the participant experiences a musculoskeletal injury during the 6-month cardiac rehabilitation program, either alternative exercises will be offered by the cardiac rehabilitation supervisor or they will be asked to discontinue the cardiac rehabilitation program until their injury heals.

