### 4.8 The identification of any data to be recorded directly on the CRFs

All patients are asked during their initial visit to TRI of whether they consent to a chart review by research personnel. All participants of the study will have provided consent to a chart review and will have study data recorded on a data collection sheet with a unique research identification number.

Data to be collected includes age, biological sex, type of PAD or CAD, diabetes status, smoking status, risk factors, current exercise regimen, medications, VO2peak, HbA1c levels, total cholesterol, blood pressure, and exercise prescription.

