### 5.2 Subject exclusion criteria.

Patients with vascular aneurysms, chronic heart failure, cancer, stroke, respiratory disease, or chronic kidney disease will be excluded. Patients with foot ulcers or skin breakdowns which may impede ability to exercise will also be excluded. Patients who cannot follow instructions in English will be excluded. Patients who attend less than 70% of sessions of the weekly sessions at TRI (<10 sessions in total) will be excluded from the main analysis and included in an intention-to-treat analysis.

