### 5.3 Withdrawal of Subjects

Participants may choose to withdraw from the study at any time. Any data collected will be discarded immediately.

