## **8.0 Statistics**

### **8.1 A description of the statistical methods to be employed**

Primary analysis to determine if patients with CAD or patients with PAD have greater improvements in  $VO_2$ peak, 6MWT, WIQ, and QOL will be tested with a series of two factor 2 (time: Baseline, End) by 2 (group: PAD, CAD) analyses of variances with Tukey's Honest Significant Difference (HSD) test for post-hoc corrections. This analysis will include patients who attended  $>70\%$  of on-site cardiac rehabilitation sessions. An intention-to-treat analysis will be conducted to include patients who attended less than 70% of the cardiac rehabilitation program sessions.

The secondary hypothesis that the magnitude of responses for patients with PAD will be dependent on biological sex will be tested through conducting a 3 factor 2 (time: Baseline, End) by 2 (group: PAD, CAD) by 2 (sex: men, women) analysis of variance. In addition to determine if the magnitude of responses are dependent on clinical presentation of PAD, a 2 factor 2 (time: Baseline, End) by 2 (type: asymptomatic, post-surgical intervention, IC) analysis of variance will be conducted.

To determine if PAD patients have greater exercising heart rate, rating of perceived exertion (Borg scale), rating of pain severity (, and training volumes than CAD patients, tertiary analysis will involve independent t-tests for these variables.

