### **8.2 The number of subjects planned to be enrolled**

Sample size calculations were conducted using an alpha of 5% and a power of 0.8. Calculations were based on the primary and secondary variables of interest ( $VO_2$ peak

Comparing the efficacy of cardiac rehabilitation for patients with peripheral artery disease to patients with coronary artery disease/Protocol #03

and 6MWT distance) for PAD and CAD patients. To be conservative, the largest sample size (6MWT) was selected.

Previous literature has found that patients with PAD undergoing exercise training compared to PAD patients who did not undergo exercise training had improvements in the 6MWT of 34.9m (95 % CI 25.6–44.1 m,  $P<0.00001$ ) (Parmenter et al., 2015). In contrast, patients with CAD had improvements of  $29.6\pm12$ m following exercise training (Jaureguizar et al., 2016). Clinically significant changes have been defined as 20m for the 6MWT (Perera et al., 2006). A difference of 10 meters between groups is a conservative average between what is observed in the literature and the defined clinically significant change. The sample size calculation for a power of 0.8 would be 23 participants per group. Accounting for a 20% drop out, 28 patients with CAD and 28 patients with PAD will be recruited. Statistical significance will be set at a  $P$  value of 0.05.

A sample size of 28 participants per group is powered to detect a difference of 1.6 ml/kg/min between groups for VO2peak.

8.3 Procedure for accounting for missing, unused, and spurious data.

If data variables are missing, the whole participant data set will be excluded from the main statistical analysis. If some data is available, the participant's data will be included in the intention to treat analysis.

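### Section 5.3 discards the data of anyone who formally withdraws, so these patients are missing from the intention-to-treat analysis as well as from the main one

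*Combined protocol and SAP*

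**What the plan says.** Section 5.3 lets participants leave at any time and then states: "Any data collected will be discarded immediately". It does not require a request, makes no exception for assessments already done, and keeps no minimum record. Section 4.7 repeats the right to withdraw and does not alter the rule.

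Section 8.3 drops anyone with missing variables from the main analysis and adds: "If some data is available, the participant's data will be included in the intention to treat analysis". Under section 5.2, patients below 70% attendance "will be excluded from the main analysis and included in an intention-to-treat analysis". Section 8.1 says the same: "An intention-to-treat analysis will be conducted to include patients who attended less than 70% of the cardiac rehabilitation program sessions". The main analysis in 8.1 is a series of group-by-time ANOVAs on baseline and end values in patients above 70% attendance.

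Section 4.1 has VO2peak, the 6-minute walk test (6MWT), SF-36 and WIQ "re-assessed at the 3 month and 6 month mark of the program", so a patient who leaves in month 4 may already have two sets of results. Section 4.8 reads "Data to be collected includes age, biological sex, type of PAD or CAD, diabetes status, smoking status, risk factors, current exercise regimen, medications" and goes on to VO2peak, laboratory values, blood pressure and exercise prescription. It lists neither date of nor reason for leaving. On numbers, section 8.2 says: "Accounting for a 20% drop out, 28 patients with CAD and 28 patients with PAD will be recruited".

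**The concern.** The main analysis is restricted to adherent patients with complete data, and the ITT analysis is the only place where the plan looks beyond them. Section 5.3 removes from it the patients who chose to leave. Whether a patient's data survive then depends on a formality rather than on clinical course.

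Two things are at stake. The ITT analysis would not be intention-to-treat for withdrawers. And nobody could check whether leavers differed from stayers at baseline or at month 3, or whether they differed in one group and not the other. Enrolled minus retained would still give a count of losses per group, but not who those patients were. That matters for a study intended to support exercise rehabilitation in PAD (section 2.2), where patients doing badly may be the ones who leave.

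**Working it through.** **1. The plan's sample size.** Inputs from section 8.2: difference 10 m, alpha 5%, power 0.8. The SD of 12 m is the only one given for the 6MWT (CAD change); its use is inferred. Two-sided normal approximation: n = 2 × (1.960 + 0.842)² × 12² / 10² = 22.6, so 23 per group, as stated. The 28 follows from 23 × 1.20 = 27.6. Losses allowed: 28 − 23 = 5 per group.

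**2. The rules applied to three patients who stop exercising in month 4.**
- *Stops attending, does not withdraw.* Out of the main analysis; some data exist, so eligible for ITT (5.2, 8.1, 8.3).
- *Says that they withdraw.* Data discarded (5.3); none are left, so out of both analyses (8.3).
- *Injured.* Section 4.7 offers other exercises, or "they will be asked to discontinue the cardiac rehabilitation program until their injury heals". This is not called withdrawal, so 5.3 does not apply.

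The first two can have the same history and the same assessments on file.

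**3. How many could be affected.** Suppose 5 per group are lost, w of them by formal withdrawal and the rest as low attenders or incomplete cases. The main set is 56 − 10 = 46 and the ITT set is 56 − 2w, so ITT adds 10 − 2w patients: 10, 6, 4 and 0 for w = 0, 2, 3 and 5. At w = 5 the two analyses use the same 46 patients and cannot disagree. The documents do not give w. The count is also nominal, because an added patient without a month-6 value contributes nothing to a Baseline/End comparison.

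**4. Dropout bias in general, for scale.** Assumptions: leavers gain nothing, and the trained-versus-untrained PAD differences that the protocol cites (34.9 m in 8.2; 0.62 ml/kg/min in 2.1 and 7.0) stand in for the gain g of PAD stayers. With k leavers of 28, the mean over all enrolled is g(28 − k)/28, so analysing stayers alone overstates it by gk/28.
- 6MWT, each excess PAD loss: 34.9/28 = 1.25 m. Five: 6.23 m, against the planned 10 m.
- VO2peak, five excess PAD losses: 0.62 × 5/28 = 0.11 ml/kg/min, about 7% of the 1.6 in 8.2 (0.11/1.6).
- Five zero-gain losses in each group: both means are multiplied by 28/23 = 1.22. With the cited gains, the 6MWT difference is 34.9 − 29.6 = 5.3 m in stayers against 5.3 × 23/28 = 4.35 m in all enrolled. If the true difference is zero, it stays zero.

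**5. What retention could recover.** Under the Baseline/End ANOVA, nothing. Take a mixed model on three visits with equal variances and equal between-visit correlation r, and let stayers have a share f of their final gain by month 3. For a zero-gain patient who leaves after month 3, the model removes a fraction f × r/(1 + r) of the bias. At an assumed r = 0.7 this is 0.21 (f = 0.5) or 0.41 (f = 1). At r = 0.94 it is 0.24 or 0.48. Section 7.0 does cite 0.94 for the 6MWT, but as test-retest reliability, not as a correlation over three months of training, so it is no more than a generous assumption here. For anyone who leaves before month 3 the fraction is 0.

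**The case against.** Deleting research data on withdrawal protects participants, and the consent pages were not available, so what participants are promised is unknown. Exposure may be narrow: 5.3 concerns withdrawal from the study, study visits coincide with standard care (4.6), and someone who quits the program need not formally withdraw. Baseline exercise testing is standard care, so the clinical chart may still hold it. Keeping the data would not by itself change any planned estimate. All of this stands. It limits the size of the problem but does not reconcile 5.3 with 8.3. No section plans to retrieve discarded values from charts, and deletion on request can be honoured without deleting everyone's data by default.

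A reader might go further in three ways that the documents do not support:
- That 5.3 causes the loss of reasons for leaving. Section 4.8 never plans to collect them, so they would be absent without 5.3 too.
- That equal losses in the two groups inflate the false-positive rate. Under the zero-gain assumption they only stretch a true difference (step 4).
- That low attenders or patients pausing for injury are deleted. They keep their data.

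**Conclusion.** The point holds as a gap in the ITT analysis. Followed as written, 5.3 and 8.3 together exclude every formal withdrawer from both analyses, and their baseline profile and any month-3 results cannot be compared with those of stayers. The size is unknown because no withdrawal rate is given, overall or by group. The upper end within the plan's own allowance is all 10 losses, with identical main and ITT sets of 46.

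The figures of about 1.2 m per excess PAD loss on the 6MWT and 0.11 ml/kg/min for five on VO2peak describe dropout bias in general, of which 5.3 is only part. They rest on zero gain in leavers and on borrowed PAD gains. It would be too strong to infer a material threat to the primary variable: on these assumptions the VO2peak effect is small. Nor would amending 5.3 alone remove the bias. What retention does allow is a description of the leavers, a sensitivity analysis that includes them, and partial recovery for those who leave after month 3.

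**What to change.** 1. In 5.3, replace the discard sentence: new collection stops at withdrawal, and data collected to that date are kept and analysed unless the participant asks for removal, in which case only a count by group is kept. Make the consent wording match.
2. In 8.1, run the ITT analysis as a group-by-time mixed model on baseline, month 3 and month 6, with a sensitivity analysis that gives leavers zero gain. The second part is needed because the mixed model assumes missing at random and recovers nothing for those who leave before month 3.
3. Tabulate baseline values of leavers beside those of stayers, by group.
4. As a separate addition to 4.8, record the date of each withdrawal and the reason if given.

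The cost is an ethics-approved amendment, one model, one small table and one line on the data sheet. No visit, test or staff is added, so the statement in 4.6 that no additional visits are required still holds. The change has to precede the first withdrawal, since discarded data cannot be restored.

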## **6.0 Study Intervention**

The study intervention is consistent with the standard 6-month out-patient cardiac rehabilitation program consists of weekly 1.5 hour visits to the TRI Rumsey Centre. After determining baseline VO2peak from the exercise stress test, an individualized walking exercise prescription will be developed by a cardiac rehabilitation supervisor which corresponds to approximately 60 to 80% of the participant's VO2peak. Participants will be invited to walk around the track and attend education sessions at the same time every week for 6 months. Patients will be encouraged to gradually increase their exercise time walking speed. Patients will be encouraged to exercise five times a week with four sessions occurring outside of the cardiac rehabilitation program.

Clinicians at TRI will record distance walked, rest periods, exercising heart rate (as palpated by the radial pulse), ratings of perceived exertion (Borg scale) and rating of pain severity on the Numeric Rating Scale for Pain (numeric scale from 0 to 10, 0 being no pain and 10 being worst pain imaginable) (Hawker, Mian, Kendzerska, & French, 2011) for each exercise session at TRI. Patients will self-record their other exercise sessions on a weekly basis using exercise diaries. Frequency, time, type, exercising heart rate and rating of perceived exertion will be recorded for each exercise session outside of TRI.

## **7.0 Assessment of Efficacy**

Peak oxygen consumption (VO2peak) measured through a treadmill test is a standard measure of cardiorespiratory fitness. A meta-regression analysis of various treadmill protocols for patients with PAD found that continuous protocols had an intraclass correlation coefficient (ICC) of 0.85 (95% CI 0.82 to 0.88) and graded protocols had an ICC of 0.83 (95% CI 0.80 to 0.85). Graded protocols were more reliable than continuous protocols for absolute claudication distance (ICC=0.95, 95% CI 0.94 to 0.96). Continuous protocols had the greatest reliability at a grade of 12 % (ICC=0.91, 95% CI 0.88 to 0.92) (Nicolai et al., 2009). In addition to being used for characteristic purposes, VO2peak can also be an outcome measure to determine the effectiveness of interventions. In a systematic review and meta-analysis, the mean difference in relative VO2peak for PAD patients who underwent exercise training compared to control patients was 0.62 ml/kg/min (95%CI 0.47 to 0.77, P<0.00001) (Parmenter et al., 2015). This suggests that VO2peak is responsive to changes following exercise interventions. It should be noted that although VO2peak is one parameter used to define intensity in exercise prescriptions, PAD patients with IC often exercise according to pain tolerance (Hamburg & Balady, 2011).

The walking impairment questionnaire (WIQ) is a validated method of quickly measuring walking ability in men and women with PAD (McDermott et al., 1998). The WIQ consists of 14 items related to walking distance, walking speed and stair climbing ability using a scale from 0 to 4 to rank degree of difficulty. An overall score below 42.5 suggests a patient with low walking ability (sensitivity 0.90, specificity of 0.73) whereas a score above 75.5 suggests a patient with a high walking ability (sensitivity 0.41, specificity 0.90) (Sagar, Brown, Zelt, Pickett & Tranmer, 2012). In a cross-sectional

Comparing the efficacy of cardiac rehabilitation for patients with peripheral artery disease to patients with coronary artery disease/Protocol #03

study validating the WIQ, the WIQ distance score was moderately correlated with 6MWT times with a Spearman rank correlation coefficient of 0.557 for patients with PAD (McDermott et al., 1998). Considering the evidence, the WIQ is a useful clinical tool to assess walking ability.

Montgomery and Gardner (1998) determined test-retest reliability using multiple 6MWT trials among 64 PAD patients. The distance walked and number of steps taken were similar between trials with a reliability coefficient of  $R=0.94$  and  $R=0.90$ , respectively. QOL can be measured through standardized general questionnaires such as the Short-Form 36 health survey (SF-36). The SF-36 is the most common instrument used to measure health related QOL in physical activity research (Hart & Kang, 2015; Novakovic et al., 2016; Stoner et al., 2016). It has high internal consistency (Cronbach's  $\alpha>0.8$ ), with the exception of social functioning likely due to having only two items in that domain ( $\alpha=0.79$ ), among older adults (Brazier et al., 1992; Walters, Munro & Brazier, 2001). A meta-analysis of the reliability of the SF-36 in physical activity research with various research designs and patient populations found strong effect sizes (ES) for physical health ( $ES=0.90$ , 95% CI: 0.88 to 0.92,  $P<0.001$ ) and mental health ( $ES=0.90$ , 95% CI: 0.89 to 0.91,  $P<0.001$ ) domains (Hart & Kang, 2015). This suggests that the SF-36 is a responsive measure of QOL for physical activity research. The SF-36 is also considered to be a suitable general measure of QOL for patients with PAD (Mehta, Subramaniam & McCollum, 2003).

## **8.0 Statistics**

### **8.1 A description of the statistical methods to be employed**

Primary analysis to determine if patients with CAD or patients with PAD have greater improvements in  $VO_2$ peak, 6MWT, WIQ, and QOL will be tested with a series of two factor 2 (time: Baseline, End) by 2 (group: PAD, CAD) analyses of variances with Tukey's Honest Significant Difference (HSD) test for post-hoc corrections. This analysis will include patients who attended  $>70\%$  of on-site cardiac rehabilitation sessions. An intention-to-treat analysis will be conducted to include patients who attended less than 70% of the cardiac rehabilitation program sessions.

The secondary hypothesis that the magnitude of responses for patients with PAD will be dependent on biological sex will be tested through conducting a 3 factor 2 (time: Baseline, End) by 2 (group: PAD, CAD) by 2 (sex: men, women) analysis of variance. In addition to determine if the magnitude of responses are dependent on clinical presentation of PAD, a 2 factor 2 (time: Baseline, End) by 2 (type: asymptomatic, post-surgical intervention, IC) analysis of variance will be conducted.

To determine if PAD patients have greater exercising heart rate, rating of perceived exertion (Borg scale), rating of pain severity (, and training volumes than CAD patients, tertiary analysis will involve independent t-tests for these variables.

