#### 3.1.1 Primary objective

The primary objective of this proposed study is to compare the magnitude of the responses to a 6-month cardiac rehabilitation program for patients with PAD in contrast to patients with CAD. The primary variable of interest will be peak oxygen consumption ( $VO_2\text{peak}$ ) with a secondary variable of interest being functional capacity, as measured by the 6-minute walk test. Tertiary variables of interest will include walking impairment, as measured by the Walking Impairment Questionnaire, and quality of life, as measured by the Short Form-36 health survey (SF-36).

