## Comparing the efficacy of cardiac rehabilitation for patients with peripheral artery disease to patients with coronary artery disease/Protocol #03

The primary endpoints of interest include change in VO2peak from month 6 to baseline, change in 6 minute walk test distance from month 6 to baseline, as well as change in walking impairment and quality of life as assessed through questionnaires from month 6 to baseline.

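### Section 8.1 does not name the paired time-by-group interaction as the deciding test, and the Tukey step it adds to the 2 x 2 ANOVA cannot supply the PAD-CAD difference in change

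*Combined protocol and SAP*

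**What the plan says.** The primary objective (section 3.1.1) is to "compare the magnitude of the responses to a 6-month cardiac rehabilitation program for patients with PAD in contrast to patients with CAD". Section 4.1 puts the endpoints on the change scale, for example "change in 6 minute walk test distance from month 6 to baseline".

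Section 8.1 introduces the "Primary analysis to determine if patients with CAD or patients with PAD have greater improvements" and specifies, for each outcome, two-factor 2 (time) by 2 (group) "analyses of variances with Tukey's Honest Significant Difference (HSD) test for post-hoc corrections". It does not mention the interaction, does not call time a repeated factor or the model mixed, and gives no error term for the ANOVA or for Tukey's procedure. It also does not say whether the post-hoc comparisons depend on a significant ANOVA result.

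Section 8.2 states: "Sample size calculations were conducted using an alpha of 5% and a power of 0.8". It uses a 10 m between-group difference in 6MWT and arrives at 23 per group, or 28 after allowing for dropout.

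**The concern.** The question is a difference between groups in change. In a 2 x 2 layout that is a single one-degree-of-freedom quantity, the time-by-group interaction. Section 8.1 leaves open two things that settle the primary conclusion.

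- **How the ANOVA is fitted.** Baseline and End come from the same patients. If the ANOVA is fitted as an ordinary two-factor analysis of four independent cells, between-patient variation enters the error and the power claimed in section 8.2 is lost.
- **Which result answers the question.** The only follow-up named is Tukey's HSD. An analyst could conclude from it that one group improved significantly and the other did not, or that the groups differ at End. Either pattern can arise when the two groups respond equally.

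**Working it through.** **Inputs.** From section 8.2: difference 10 m; SD of change 12 m (the CAD figure 29.6 ± 12 m, read as an SD and applied to both groups); 23 evaluable per group; alpha 5%, taken as two-sided because that reproduces the stated number; power 0.8. The baseline-End correlation r is not given. I use 0.80, 0.90 and 0.94 as assumptions. Section 7.0 reports 0.94 for 6MWT, but as repeat-trial reliability, not as a six-month correlation. Data are taken as normal with equal variances. Simulated figures use 20,000 trials per setting.

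**1. The plan's own figure.** For a two-group comparison of mean change, n = 2(1.960 + 0.842)² × 12² / 10² = 22.6, so 23 per group. This matches section 8.2. With 23 per group the t-test on change has 79% power. With complete data that t-test is identical to the interaction test of a repeated-measures 2 x 2 ANOVA. Its simulated type I error is about 5%.

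**2. What Tukey compares.** Each factor has two levels, so Tukey is not needed for the main effects and can act only on the four cell means. The six pairs are two within-group changes, two between-group differences at one time point, and two diagonals. None is (CAD End − CAD Baseline) − (PAD End − PAD Baseline).

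**3. Unpaired fit, true difference 10 m.** A change SD of 12 m implies a cell SD of 12/√(2(1 − r)).

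- The true standard error of the difference in change is √(2 × 12²/23) = 3.54 m.
- The unpaired ANOVA instead uses 2 × cell SD/√23, and rejects beyond 1.987 times that (88 df).

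**4. Tukey's End contrast with the within-patient error, equal gains and equal baselines.**

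- The critical difference is 3.776 × (12/√2)/√23 = 6.68 m.
- The true standard error of the End difference is cell SD × √(2/23).
- At r = 0.94 this is 34.64 × 0.295 = 10.2 m. The false-positive rate is then P(|Z| > 6.68/10.2 = 0.65), about 51%, close to the simulated 52%.

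| Assumed r | Cell SD (m) | Unpaired rejection threshold (m) | Unpaired interaction power (simulated) | False End difference, read alone (simulated) |
|---|---|---|---|---|
| 0.80 | 18.97 | 15.7 | 7% | 24% |
| 0.90 | 26.83 | 22.2 | about 0% | 40% |
| 0.94 | 34.64 | 28.7 | about 0% | 52% |

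Both effects shrink if r is lower. At r = 0.5 the cell SD is 12 m and the unpaired threshold is 1.987 × 2 × 12/√23 = 9.9 m, so power is about 51%. The false End rate is then P(|Z| > 6.68/3.54 = 1.89), about 6%.

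**5. Tukey with the pooled cell error.** The End contrast is no longer too liberal, but the pairing is lost for the within-group changes. At r = 0.94 the critical difference is 3.704 × 34.64/√23 = 26.8 m, against 6.7 m with the within-patient error. With a true gain of 29.6 m in both groups, exactly one group is then flagged in about 22% of trials. At assumed cell SDs of 60 to 100 m neither group's gain is flagged in practice. So neither error term suits all six contrasts.

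**6. Tukey read only after a significant paired interaction.** The false End difference falls to about 2 to 3% across the three correlations, below the interaction's own 5%.

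**The case against.** The strongest reply is that section 8.1 tests improvement with the ANOVA and uses Tukey only post hoc. A 2 x 2 ANOVA already contains the interaction, and with time as a within-patient factor that interaction is exactly the difference in change. The endpoints in section 4.1 and the sample size in section 8.2 both point to that test, and a Baseline/End factor on the same patients is ordinarily fitted as repeated.

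Most of this stands. A reader might infer that the planned primary analysis gives a wrong answer, or that the 80% power is already lost. The documents support neither: the unpaired fit is one reading of an unspecified model, and the 24 to 52% rates require the interaction result to be ignored, which section 8.1 does not say will happen.

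Nor should much weight go on a VO2peak illustration in which equal gains leave exactly one group significant in 36% of trials. That figure assumes a gain of 1.5 ml/kg/min in both groups, 22 per group, the within-patient error, and a change SD of about 2.1 worked back from the 1.6 ml/kg/min in section 8.2. At gains the documents do report, it is about 20% (0.62) or under 1% (2.45).

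The reply does not remove the ambiguity. Section 8.1 describes an ordinary two-factor ANOVA, states no gating, and attaches a procedure that assumes independent cells to data that are not independent.

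**Conclusion.** The point holds as a should-fix. The trial was sized for the paired interaction, but section 8.1 neither names that test nor says that time is within-patient, and the post-hoc method it does name does not suit the design. For a true 10 m difference, the paired interaction has about 79% power. The unpaired fit that the wording permits has about 7% at r = 0.8 and about 0% at r = 0.9. The Tukey step cannot provide the primary answer and can mislead if read on its own, but not materially if it is read only after a significant interaction.

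The 79% rests on section 8.2's 10 m and on 12 m as the SD of change in both groups. The unpaired power and the Tukey error rates also rest on the assumed correlations.

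**What to change.** In section 8.1:

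- State that, for each outcome, the primary PAD-CAD comparison is the time-by-group interaction of a repeated-measures (mixed) model with time as a within-patient factor. Equivalently, it is the between-group difference in month-6-minus-baseline change. Report it as a mean difference with a 95% CI.
- Delete Tukey's HSD from the 2 x 2 analyses.
- Report within-group changes descriptively with CIs, and state that significance in one group and not in the other is not evidence of a difference in response.

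The cost is wording only. No new data are needed, and the calculated 23 per group and the planned 28 per group stay as they are.

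### The primary PAD-CAD comparison is conditional on attendance observed after enrolment; the analysis that restores low attenders is planned but ranks second

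*Combined protocol and SAP*

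**What the plan says.** Section 8.1 calls the 2 by 2 (time by group) analysis of variance the primary analysis and sets its population: "This analysis will include patients who attended" more than 70% "of on-site cardiac rehabilitation sessions". Section 5.2, under the exclusion criteria, gives the rule with a second cut-off: "Patients who attend less than 70% of sessions of the weekly sessions at TRI (<10 sessions in total) will be excluded" from the main analysis. Section 2.4 repeats it.

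The excluded patients are not lost altogether. Section 5.2 says that they "will be excluded from the main analysis and included in an intention-to-treat analysis", and 8.1 adds: "An intention-to-treat analysis will be conducted to include patients who attended less than 70" per cent of sessions.

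Four other provisions bear on who is analysed:

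- **4.7.** "If the participant experiences a musculoskeletal injury during the 6-month cardiac rehabilitation program", there are two options: "either alternative exercises will be offered by the cardiac rehabilitation supervisor", or the participant is asked to pause until recovered.
- **5.3.** Data from anyone who withdraws are discarded.
- **8.3.** A participant with missing variables is dropped entirely from the main analysis, and enters the intention-to-treat analysis if some data exist. No method is given for a missing month-6 value.
- **5.1.** PAD and CAD patients are matched at entry on sex, age, diabetes, smoking status and supervisor, as the stated control for confounding.

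**The concern.** Section 3.1.1 sets out to "compare the magnitude of the responses to a 6-month cardiac rehabilitation program for patients with PAD in contrast to patients with CAD", and the rationale in 2.2 asks whether rehabilitation is as effective in PAD as in CAD. Attendance is partly a response to the program. Section 3.2 expects more pain and higher perceived exertion in PAD, and section 7.0 notes that patients with claudication often exercise to pain tolerance. It is therefore plausible that the attendance rule removes different numbers, and different kinds, of patients from the two groups.

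If it does, the main result compares good attenders with PAD to good attenders with CAD. It leaves out part of any disease difference that operates through failure to keep attending. Removal after enrolment also breaks the matched sets, and the analysis of variance in 8.1 names no covariates to compensate.

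Nothing else planned would clearly show the problem. The exploratory comparison of training load reflects exercise frequency, but no section plans a report by group of how many fall below the cut, or why.

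**Working it through.** **1. The plan's own figure.** Section 8.2 uses a 10 m difference on the 6-minute walk, alpha 5% and power 0.8. It cites a change of 29.6 ± 12 m in CAD; the ± is unlabelled and is read here as the SD of change. Two-sided:

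n = 2 × (1.96 + 0.84)² × 12² / 10² = 22.6, so 23 per group, as stated. Then 23 × 1.2 = 27.6, so 28, also as stated. (Dividing by 0.8 would give 29.)

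The 10 m design difference is the yardstick below.

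**2. What the attendance rule removes.** Weekly visits for 6 months are taken as 24 to 26 sessions (assumption).

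| Sessions offered | 70% of sessions | Needed to exceed 70% | Most that can be missed |
|---|---|---|---|
| 24 | 16.8 | 17 | 7 |
| 25 | 17.5 | 18 | 7 |
| 26 | 18.2 | 19 | 7 |

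Under the percentage reading, missing 8 or more sessions removes a patient, so an 8-week injury pause is enough.

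Under the reading of fewer than 10 sessions, a patient with 10 stays in and may have missed 14 to 16. An 8-week pause then removes nobody. Ten sessions are 10/26 = 38% to 10/24 = 42% of the program, and would be 70% of only about 14 sessions (10/0.70 = 14.3). The two cut-offs select different patients and must be reconciled. Either one selects after enrolment.

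**3. How much the main result could differ from the all-enrolled result.** Suppose attenders in both groups gain the same amount m, so that the main analysis shows 0 m. Non-attenders gain a fraction f of m, and the non-attendance proportions are p(PAD) and p(CAD). The all-enrolled CAD-minus-PAD difference is then

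D = [p(PAD) − p(CAD)] × (1 − f) × m.

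For m, section 8.2 offers 29.6 m (change in CAD) and 34.9 m (PAD, against untrained controls). The rates and f are assumptions. The low end uses m = 29.6 and f = 0.5; the high end uses m = 34.9 and f = 0.

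| Non-attendance, PAD vs CAD | Low end | High end |
|---|---|---|
| 20% vs 20% | 0 m | 0 m |
| 20% vs 10% | 0.10 × 0.5 × 29.6 = 1.5 m | 0.10 × 34.9 = 3.5 m |
| 30% vs 10% | 0.20 × 0.5 × 29.6 = 3.0 m | 0.20 × 34.9 = 7.0 m |
| 40% vs 10% | 0.30 × 0.5 × 29.6 = 4.4 m | 0.30 × 34.9 = 10.5 m |

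If CAD patients were the poorer attenders, the sign would reverse.

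**4. Power if everyone enrolled is analysed.** Power = Φ(10 / [12 × √(2/n)] − 1.96). With n = 28 per group and complete month-6 data this is 87.7%. With 20% loss, about 22 per group, it is 78.9%. Both assume that the 10 m difference and the SD of 12 m are unchanged.

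**The case against.** The strongest reply is that the restriction reflects a choice of question. The study is a non-randomised cohort with groups set by referring diagnosis, so an intention-to-treat analysis preserves no randomisation. The title and 3.1 speak of efficacy, and a comparison among those who received the program is a legitimate reading. This stands in part: the restricted analysis deserves a place. It does not justify making that analysis primary, because 2.2 asks the broader question and because selection on attendance undoes the entry matching, the plan's only stated control for confounding.

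Several stronger readings are tempting, and the documents do not support them:

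- **That patients told to stop for injury are removed.** Section 4.7 removes no one from the analysis. The pause is temporary and one of two options, and it matters only if attendance falls below the cut or data go missing. Nor does 4.7 say that the program caused the injury; it refers to injury arising during it.
- **That low attenders disappear from the results.** They return in a planned second analysis.
- **That the plan leaves open which result governs.** The restricted analysis is labelled primary in 8.1 and main in 2.4 and 5.2.
- **That PAD patients will attend less.** Section 3.2 predicts more pain and exertion but does not link them to attendance, and no rates are given.

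It is also fair to say that zero gain in non-attenders is extreme, since four of the five weekly sessions are off-site. The illustration covers the 6-minute walk only, which 3.1.1 ranks after VO2peak.

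**Conclusion.** The concern holds as a matter of which analysis is primary. The main comparison is conditional on a post-enrolment variable that may depend on disease, and the analysis that corrects this ranks second. That second analysis is itself incomplete, because withdrawers' data are discarded and no method is given for missing month-6 values.

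The size cannot be known from the documents. On the 6-minute walk it is 0 m at equal non-attendance, and about 1.5 to 10.5 m under the assumed rates and gains; only the most extreme case reaches the 10 m design difference. These figures rest on equal gains among attenders and on invented non-attendance rates. They do not carry over to VO2peak. Long injury pauses can contribute under the 70% cut-off. Under the 10-session cut-off an 8-week pause does not.

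**What to change.** - **5.2 and 8.1 (and the repeat in 2.4):** make the analysis of all enrolled participants, regardless of attendance, the main analysis on which the conclusion rests. Keep the attendance-restricted analysis as a named supportive analysis. Move the attendance sentence out of the exclusion criteria, and reconcile the 70% and 10-session cut-offs.
- **8.3:** replace whole-participant deletion in the main analysis with a method that uses all available baseline, month-3 and month-6 data, for example a mixed model for repeated measures. Section 4.1 already schedules the month-3 measurements.
- **5.3:** distinguish stopping the program from withdrawing consent to data use, so that people who only stop attending remain in the analysis.
- **Reporting:** give the number below the attendance cut in each group, with reasons for absence where recorded. The data list in 4.8 does not include reasons, so a field would have to be added.

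Both analyses are already planned, but this is more than a change of wording: it needs a missing-data method and some extra recording. The headline effect will probably be somewhat smaller and more variable than among good attenders.
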